Appendix 1. Abbreviations

The following is a list of abbreviations that may be used in the protocol.

Abbreviation	Term
Abs	absolute
AE	adverse event
ALT	alanine aminotransferase
ANCOVA	analysis of covariance
AST	aspartate aminotransferase
AUC	area under the curve
BBS	Biospecimen Banking System
BID	twice daily
BMI	body mass index
BP	blood pressure
CI	confidence interval
CL	Plasma clearance
Cmax	maximum observed concentration
CRF	case report form
CS	compound symmetric
CSA	clinical study agreement
CSR	clinical study report
CT	clinical trial
CTA	clinical trial application
CYP	cytochrome P450
DILI	drug-induced liver injury
DMC	data monitoring committee
CCI	
EC	ethics committee
ECG	electrocardiogram
EDP	exposure during pregnancy
CCI	
EDTA	edetic acid (ethylenediaminetetraacetic acid)
EPB	echo poor band
EU	European Union
EudraCT	European Clinical Trials Database
FAS	full analysis set
FSH	follicle-stimulating hormone
GCP	Good Clinical Practice
GGT	gamma-glutamyl transferase
HepBcAb	hepatitis B core antibody
HepBsAg	hepatitis B surface antigen
HCVAb	hepatitis C antibody
HIV	human immunodeficiency virus

Abbreviation	Term
ICH	International Conference on Harmonisation
ID	identification
IL	interleukin
IND	investigational new drug application
INR	international normalized ratio
IP	Investigational Product
IRB	institutional review board
ITT	intent-to-treat
IUD	intrauterine device
K ₂ EDTA	dipotassium ethylenediaminetetraacetic acid
LFT	liver function test
LOCF	last observation carried forward
LSLV	last subject last visit
MCH	mean corpuscular hemoglobin
MCHC	mean corpuscular hemoglobin concentration
MCV	mean corpuscular volume
N/A	not applicable
NOAEL	no observed adverse effect level
PCD	primary completion date
CCI	
PE	physical examination
PI	principal investigator
PK	pharmacokinetics
PPS	per protocol set
PPT	psoriasis plaque test
PR	pulse rate
PT	prothrombin time
PUVA	phototherapy/psoralen+UVA
QTc	corrected QT
qual	qualitative
RBC	red blood cell
CCI	
RORC2	retinoid acid-related orphan receptor 2
SAE	serious adverse event
SAP	statistical analysis plan
SD	standard deviation
SRC-1	steroid receptor coactivator-1
SRSD	single reference safety document
TEAE	treatment emergent adverse event
TBili	total bilirubin
Th17	T helper 17
THC	tetrahydrocannabinol

Abbreviation	Term
TNF	tumor necrosis factor
ULN	upper limit of normal
UN	unstructured
US	United States
UV	ultraviolet
V_{ss}	steady state volume of distribution
WBC	white blood cell

1. AMENDMENTS FROM PREVIOUS VERSION(S)

None.

2. INTRODUCTION

RORC2 is a transcription factor that controls the production of the cytokine IL-17A, which plays a central role in the pathogenesis of psoriasis. Psoriasis lesions contain prominent inflammatory cell infiltrates that include T cells that produce IL-17A. PF-06763809 inhibited the binding of purified recombinant human RORC2 ligand binding domain steroid receptor coactivator-1 (SRC-1) with an IC₅₀ value of 3.1nM. In vivo studies data suggest that topical PF-06763809 inhibited the production of IL-17A in mouse models to an extent that was sufficient to cause a reduction in inflammation which was similar to neutralization of IL-17A by anti-IL17A mAb.

[figure not shown]
Inhibition of RORC2-mediated inflammation has the potential to provide a novel approach in the topical treatment of plaque psoriasis. This first-in-human study will evaluate PF-06763809 solution, applied topically to skin surface areas in subjects with chronic mild to moderate plaque psoriasis. The primary study objective using the psoriasis plaque test (PPT) is to assess the reduction in psoriatic skin infiltrate thickness/ echo poor band (EPB) as a measure of disease activity in response to study treatment; appropriate vehicle and active controls (calcipotriene/calcipotriol and betamethasone) will also be included. Safety and tolerability of PF-06763809 solution applied topically will also be assessed. Evidence of short-term clinical activity with PF-06763809 will systematically inform subsequent development of a formulation more suitable for topical use.

2.1. Study Design

The study is proposed as a randomized, double-blinded, vehicle and active comparator-controlled, multiple dose study in subjects with psoriasis. A total of approximately 15 subjects with chronic plaque type psoriasis and with a treatment area sufficient for 6 treatment fields on 1 to 3 comparable plaques defined as having treatment fields with psoriatic skin infiltrate thickness/EPB of at least 200 μ m will be randomized. Subjects will receive topical doses (2.3%, 0.8% and 0.23%) of PF-06763809, PF-06763809 vehicle, and two active comparators (calcipotriene/calcipotriol and betamethasone) in this study. Each eligible subject will receive six treatments at six different test fields in a random order. The effect of the PF-06763809 solutions will be assessed in comparison to the corresponding vehicle, calcipotriene/calcipotriol and betamethasone solutions using the PPT, which also allows within subject comparison of treatments.

The overall study design is summarized in Figure 1.

Figure 1. Overall Study Design

2.2. Study Objectives

2.2.1. Primary Objectives

- *To assess the changes in psoriatic skin infiltrate thickness/EPB in response to PF-06763809 2.3%, 0.8% and 0.23% applied topically for 18 consecutive days as compared to the vehicle control.*
- *To determine the safety and tolerability of multiple dose topical administration of PF-06763809 in psoriasis subjects.*

2.2.2. Secondary Objectives

- *To evaluate the Area Under the Curve (AUC) of psoriatic skin infiltrate thickness/EPB for PF-06763809 compared to vehicle.*
- *To assess the effect of PF-06763809 compared to calcipotriene/calcipotriol solution in the change of psoriatic skin infiltrate thickness/EPB both within and following 18 days of treatment.*
- *To assess the effect of PF-06763809 compared to betamethasone solution in the change of psoriatic skin infiltrate thickness/EPB both within and following 18 days of treatment.*

CCI

- 
- 
- 
- 
- 

3. INTERIM ANALYSES, FINAL ANALYSES AND UNBLINDING

No formal interim analysis will be conducted for this study.

This is a randomized double-blind study. Subjects are blinded to the treatment sequence throughout the study. Investigators will be blinded to the treatment sequence, except exceptional circumstances when knowledge of the actual treatment code is absolutely essential for management of the subject. Blinded personnel performing the CCI  ultrasound measurements should not be present during the treatment application procedures in order to remain blinded.

It is anticipated that a limited number of site staff administering the treatments will be unblinded. Other investigator site staff and Pfizer study team will be blinded to study treatment sequence. The blinded study monitor, if assigned, will remain blinded to treatment until all monitoring of the study has been completed.

To minimize the potential for bias, treatment randomization information will be kept confidential will not be released to the blinded investigator or blinded investigator site staff until the study database has been locked or the investigator requests unblinding of individual subjects for safety reasons.

Study unblinding will not be performed until the final database has been locked for all subjects. Final analysis will follow the official database release.

4. HYPOTHESES AND DECISION RULES

4.1. Statistical Hypotheses

This study is designed to show that PF-06763809 has a superior effect against vehicle in the primary endpoint of relative change from baseline in infiltrate thickness at Day 19. The following hypotheses will be formally tested first under a significance level of 5% (two-sided):

- The null hypothesis (H_{01}): PF-06763809 has no greater reduction from baseline in infiltrate thickness at Day 19 than vehicle.
- The alternative hypothesis (H_{11}) is that PF-06763809 has a greater reduction from baseline in infiltrate thickness at Day 19 than vehicle.

If the null hypothesis H_{01} is rejected statistically, then the following hypotheses will be formally tested next under a significance level of 5% (two-sided):

[figure not shown]
- The null hypothesis (H_{02}): PF-06763809 has no greater reduction from baseline in infiltrate thickness at Day 19 than calcipotriene/calcipotriol.
- The alternative hypothesis (H_{12}) is that PF-06763809 has a greater reduction from baseline in infiltrate thickness at Day 19 than calcipotriene/calcipotriol.

[figure not shown]
Data from three psoriasis plaque test (PPT) studies conducted at bioskin® GmbH were used to generate the assumption for sample size calculation. In these three studies, the calcipotriene/calcipotriol solution demonstrated 36% - 44% reduction in infiltrate thickness relative to vehicle. The observed within-subject standard deviation (SD) estimates for calcipotriene/calcipotriol solution relative to vehicle ranged from 0.331-0.435. Power analyses were performed for samples sizes of N=15 and N=20 under within-subject SDs of 0.38, 0.435 and 0.5 with 2-sided type-I error rate of 5% and results were summarized C

CCI

I.

CCI

CC1

A large blacked-out rectangular area representing a redacted section of the document, likely containing sensitive information.

4.2. Statistical Decision Rules

The primary endpoint for this study is the change relative to baseline in psoriatic skin infiltrate thickness/EPB at Day 19 [REDACTED] for PF-06763809 in comparison to vehicle. The efficacy assessment of PF-06763809 will be performed for the change from baseline in log of the psoriatic skin infiltrate thickness/EPB on Day 19 using a longitudinal analysis of covariance model, with treatment, visit, treatment by visit interaction as main effects and the log of the psoriatic skin infiltrate thickness/EPB at baseline as covariate. The point estimate and 95% confidence interval (CI) for the difference in log transformed means at Day 19 visit between treatment groups will be constructed using least square means and appropriate standard errors. The assessment of the primary endpoint will be performed at a two-sided significance level of 0.05.

5. ANALYSIS SETS

5.1. Full Analysis Set

All subjects, who have at least one application of the investigational products and have at least one post-baseline assessment of the primary efficacy variable, will be included in the Full Analysis Set (FAS).

5.2. Per Protocol Set

The Per Protocol Set (PPS) is a subset of the FAS. Subjects with major protocol deviations and subjects who discontinued the study prematurely will be excluded from the PPS. The key protocol violators will follow the procedure outlined in Section 5.7 below.

CCI [REDACTED]

[REDACTED]

CCI [REDACTED]

[REDACTED]

5.5. Safety Analysis Set

Safety analysis will be performed for all subjects who had any investigational product dispensed. Subjects will be analyzed according to the treatment they are actually received.

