Approximately 180 μL of each liquid preparation and 180 μL of each comparator will be applied CCI [REDACTED] under Duhring[®] chambers (12 mm inside diameter, 14 mm outside diameter) seated in holes punched in hydrocolloid dressing (eg, Varihesive[®], Bristol-Myers Squibb Gruppe, Munich, Germany). The fields will be treated under occlusion for 18 days. Subjects will return daily to the center for re-application of the test substances daily during the 18-day treatment period. Before each new application any remaining residue of the previously applied preparation will be removed gently by cleansing each test field with a clean soft tissue. Following this regimen, each preparation will be left in contact with lesional skin under a Duhring[®] chamber until removal for inspection at the next visit. This ensures that there is exposure to each preparation almost continually for the 18 days of the treatment phase of the study.

CCI

Safety will be assessed by monitoring of vital signs, safety laboratory tests (see [Section 7.1.4](#) and [7.1.1](#) respectively) and by recording of adverse events (AEs) and serious adverse events (SAEs) (see [Section 8](#)). Special attention will be given to local safety (ie, signs of skin irritation at the application sites). Skin reactions will be recorded as AEs.

The overall study design is summarized in Figure 1.

Figure 1. Overall Study Design

In this study, subjects who prematurely discontinue for non-safety related reasons may be replaced, at the discretion of the Sponsor. Up to 5 subjects may be replaced.

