3.2. Stopping Rules for Dosing in Individual Subjects

At investigator discretion, for subjects' safety, dosing with any or all double-blinded investigational product/s, may be stopped in an individual subject – either temporarily or permanently. In such cases, any open TEAEs (treatment emergent adverse events) must be followed to resolution or until such time that the event is viewed to have stabilized – refer to [Section 8](#) for details.

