5.1. Allocation to Treatment

The investigator's knowledge of the treatment should not influence the decision to enroll a particular subject or affect the order in which subjects are enrolled.

Each eligible subject will receive six treatments at six different test fields in a random order. There will be no subdivision into treatment groups.

The test fields will be numbered 1-6. As far as possible the following procedure for numbering will be followed: The numbering should begin with the uppermost or most proximal site on the left from the investigator's view. Fields along the same line should be numbered from left to right. If more than one plaque is included, numbers for the fields on the next plaque will be assigned likewise starting with the next free number. The exact location of each test field in relation to the outline of the plaque(s) will be traced on a transparent plastic sheet which will be kept with the subject's source data. The location of the test fields will be documented in the Case Report Form (CRF) as:

Upper/lower left/right arm,

Upper/lower left/right leg,

Front/back trunk.

At screening, a subject will be assigned a subject number. Once the subject meets all eligibility criteria, the subject will be randomized into the study according to the randomization schedule, which is generated through the Pfizer randomization system. Randomization will be performed by permutation of the six treatments. At randomization, each eligible subject will be assigned a randomization number, which corresponds to a random permutation of six treatments. The treatment listed first in the respective treatment sequence will be assigned to test field number 1, the second treatment to test field number 2, etc.

Subjects are blinded to the treatment sequence throughout the study. Investigators will be blinded to the treatment sequence except exceptional circumstances described in [Section 5.2](#). Limited site staff who administer the treatments will be unblinded.

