5.5. Administration

The dosing volume for all study treatments is 180 µL (164 µL/cm²), applied topically once daily to 1.1 cm² skin surface area during an 18 day treatment period. Hence, subjects will be exposed to:

Study Treatment 1:

2.3% PF-06763809 solution

Daily dosage: approximately 4.1 mg PF-06763809

CCI

Study Treatment 2:

0.8% PF-06763809 solution.

Daily dosage: approximately 1.4 mg PF-06763809

CCI

Study Treatment 3:

0.23% PF-06763809

Daily dosage: approximately 0.41 mg PF-06763809

CCI

Study Treatment 4 (vehicle):

Active ingredient-free vehicle to PF-06763809 treatments

Study Treatment 5 (positive control):

Calcipotriene/ calcipotriol (50 µg/mL)

Daily dosage of calcipotriol: approximately 0.01 mg

CCI

Study Treatment 6 (positive control):

Betamethasone (1 mg/g)

Daily dosage of approximately 0.18 mg

CCI

All subjects will receive each study treatment once daily. All study treatments will be applied by way of Duhring® chambers seated in holes punched in a hydrocolloid dressing (eg, Varihesive® E [Convatec], Munich, Germany). The hydrocolloid dressing will be fixed on the skin with adhesive patches (eg, BSN Medical, Hamburg, Germany, or comparable) containing the same holes for the chambers as the hydrocolloid dressing. CCI

The filled chamber will then be placed on the skin at the location of the relevant test fields. After each test chamber is filled with the appropriate volume, the test chambers will be subsequently applied to the test fields.

The chambers will be fixed in place with Leukosilk® (eg, BSN, Hamburg, Germany or comparable) and will be removed before each new application. In previous studies the hydrocolloid dressing has been shown to be well tolerated. The lack of a therapeutic influence of the dressing on the psoriasis has been verified by determination of the psoriatic skin infiltrate thickness/EPB before and after application. CCI

The fields will be treated with occlusion for a treatment period of 18 days (Day 1 through 18). Before each new application remaining preparation residues will be removed by gently cleansing each test field with a separate soft tissue. The hydrocolloid dressing will be renewed on Days 1 and all subsequent CCI measurement days or as necessary.

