5.6. Treatment Misallocations

If a subject takes a treatment that is not consistent with the treatment they are randomized to, then they will be reported under their randomized treatment group for efficacy analyses, but will be reported under treatment they actually received for all other analyses.

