8.2. Safety Analysis

The safety endpoints described in [Section 6.2](#) will be listed and summarized in accordance with sponsor reporting standards, where the resulting data presentations will consist of subjects from the safety analysis set.

AEs, ECGs, BP, PR, and safety laboratory data will be reviewed and summarized on an ongoing basis during the study to evaluate the safety of subjects. Any clinical laboratory, ECG, BP, and PR abnormalities of potential clinical concern will be described. Safety data will be presented in tabular and/or graphical format and summarized descriptively, where appropriate.

Medical history and physical examination and neurological examination information, as applicable, collected during the course of the study will be considered source data and will not be required to be reported, unless otherwise noted. However, any untoward findings

identified on physical and/or neurological examinations conducted during the active collection period will be captured as AEs, if those findings meet the definition of an AE. Data collected at screening that are used for inclusion/exclusion criteria, such as laboratory data, ECGs, and vital signs, will be considered source data, and will not be required to be reported, unless otherwise noted. Demographic data collected at screening will be reported.

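### Does the SAP's treatment-received rule for safety break down when every subject gets all six products?

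*SAP*

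**What the plan says.** SAP 5.5 admits to the safety set every subject who had investigational product dispensed, and adds: "Subjects will be analyzed according to the treatment they are actually received". SAP 5.6 keeps misallocated subjects in their randomized group for efficacy, "but will be reported under treatment they actually received for all other analyses". SAP 8.2 says that the safety endpoints "will be listed and summarized in accordance with sponsor reporting standards"; it does not mention test fields.

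The design is within-subject. Protocol 5.5 states: "All subjects will receive each study treatment once daily". Protocol 5.1 states: "There will be no subdivision into treatment groups". It also fixes how products reach the skin: "The treatment listed first in the respective treatment sequence will be assigned to test field number 1", and so on through field 6.

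Safety and tolerability form one of the two primary objectives. Protocol 3.1 records skin reactions as adverse events and says: "Special attention will be given to local safety (ie, signs of skin irritation at the application sites". Under Protocol 3.2, "dosing with any or all double-blinded investigational product/s, may be stopped in an individual subject".

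**The concern.** Sections 5.5 and 5.6 of the SAP read as if each subject had one treatment and belonged to one randomized group. Here every subject has six treatments, and the protocol says there are no groups. Taken word for word, the rule puts every event under every product and cannot separate the test drug from vehicle or from the active comparators.

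That would matter most for application-site reactions. These are the one kind of safety event that this design can tie to a product, because each field carries only one. Protocol 1.2.3 reports mild to moderate skin irritation from the vehicle in the nonclinical studies, so local reactions on the test drug need to be read beside those on vehicle. A literal table would erase that comparison. It would also suggest a by-product attribution of systemic findings that simultaneous exposure to six products cannot support. A subject-level list of products received would also miss a swap of two chambers.

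**Working it through.** The plan states no figure on this point, so there is none to reproduce. The check sets the two readings of the rule side by side.

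**Inputs**
- Products and fields per subject: 6 and 6 (Protocol 5.1; SAP 2.1).
- Subjects: about 15 completers (Protocol 9.1); up to 5 replacements (Protocol 3.1 and 6.4).
- Assignment: a random permutation of the six products, matched in order to fields 1 to 6 (Protocol 5.1).

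**1. Units.** 15 × 6 = 90 treated fields, 15 per product. With all 5 replacements, 20 × 6 = 120 fields, 20 per product.

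**2. One reaction at one field**

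| Reading | Entries in the table | Entries naming a product not applied there |
|---|---|---|
| Subject-level, literal | 6 entries of 1/15 | 5 of 6 (83%) |
| Field-level | 1 entry of 1/15 | 0 |

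The literal reading gives six identical columns whatever the data show. A table that cannot differ between columns is not one that anyone would produce or interpret.

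**3. A swap of two chambers.** Let the randomized sequence be A, B, C, D, E, F and the applied sequence B, A, C, D, E, F.
- As an unordered list of products, 0 of 6 entries differ.
- As an ordered sequence, 2 of 6 positions differ.

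Protocol 5.1 defines the assignment as the ordered sequence, and SAP 3 likewise refers to blinding of the treatment sequence. A swap is therefore a departure from what was randomized, and SAP 5.6 applies to it: the two fields are reported for safety under the products actually applied.

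**4. Systemic data.** SAP 8 gives descriptive summaries by treatment group only where that applies, and Protocol 5.1 says there are no groups. Protocol 9.6 has no by-treatment rule. Nothing visible directs laboratory, ECG, vital-sign or systemic event data into six columns.

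**5. Precision.** For no reactions among the fields of one product, the exact two-sided 95% upper limit is 1 − 0.025^(1/n):
- n = 15: 21.8%
- n = 20: 16.8%

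These limits follow from the number of subjects. Rewording SAP 5.5 or 5.6 would not change them.

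**6. Where the literal reading would mislead most.** The worst case is a reaction confined to the vehicle field. Protocol 5.5 describes Treatment 4 as the vehicle of the test-drug solutions without the active ingredient, so vehicle is present on 4 of the 6 fields (three strengths plus vehicle alone). Irritation caused by the vehicle would be expected on all four, so a large vehicle-only excess is not a realistic example.

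**The case for a change.** The strongest case for a change is that a prespecified plan should not lean on the analyst's good sense for a primary objective. Skin reactions are captured as adverse events, so attribution of those events decides the local tolerability result. The visible adverse event sections of the protocol (8.1 to 8.1.5) do not ask for a field number. If the case report form also omits it, the link from reaction to product could be hard to recover afterwards. The remedy would be a few words and at most one data item.

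Part of this stands. The wording of SAP 5.5 and 5.6 does not fit the design, 5.6 refers to a randomized group that does not exist, and the visible SAP never names the test field as the unit for site reactions.

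The consequence does not stand. It needs a reading that contradicts Protocol 5.1 and produces six identical columns. The worry about the form cannot be settled from these documents, because the adverse event page is not shown. What can be seen points the other way: field locations are documented in the case report form (Protocol 5.1), and stopping a single product in a subject (Protocol 3.2) presupposes that the site can say which field is affected. Several SAP and protocol sections on endpoints and assessments are blacked out, and the sponsor's reporting standards are not available, so a field-level rule may already exist.

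**Conclusion.** No change is needed. The mismatch is real but is one of wording: standard parallel-group sentences carried into a within-subject plan, leaving a detail unstated. Read with Protocol 5.1, the treatment received is the product applied at a field. That reading counts each site reaction once and brings a chamber swap within SAP 5.6.

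The stakes are limited. Safety is descriptive, with about 15 fields per product and no planned safety test. The primary efficacy model (SAP 8.1) already handles treatment as a within-subject factor and does not use these rules. Listings are also planned, so a site reaction recorded with its field can be traced to its product through the randomization and dosing records.

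This rests on two assumptions: that the analyst follows the protocol's definition of the assignment, and that the record of a site reaction identifies the field. The visible documents support the first directly and the second indirectly; they contradict neither.
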